**Table 7 Guideline for treatment of patients experiencing adverse events**

Recommended dose modifications for pasireotide/ placebo	
Worst toxicity CTCAE Grade* (value)	Recommended dose modification any time during a cycle of therapy
No toxicity	Maintain dose level
Hematologic	
Neutropenia (ANC)	
Grade 1 (ANC < LLN - 1500/mm  )	Maintain dose level
Grade 2 (ANC < 1500 - 1000/mm  )	Maintain dose level
Grade 3 (ANC < 1000 - 500/mm  )	Omit dose until resolved to ≤ Grade 2, then ↓ 1 dose level 
 
• If resolved ≤ 7 days, then maintain dose level
 
• If resolved > 7 days, then ↓ 1 dose level
 

Grade 4 (ANC < 500/mm  )	Omit dose until resolved to ≤ Grade 2, then ↓ 1 dose level 
 
• If resolved ≤ 7 days, then maintain dose level
 
• If resolved > 7 days, then ↓ 1 dose level
 

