## 6.6 Pasireotide LAR / placebo dose adjustment

As already described above, pasireotide LAR/placebo at 60 mg every 28 days is the recommended starting dose for oncological indications (including NETs). If tolerability issues occur, the treatment dose may be reduced to pasireotide LAR at 40 mg with next scheduled injection. Patients requiring a dose reduction can return to the higher dose once the tolerability issue is resolved. However, patients not able to tolerate the minimum pasireotide LAR dose of 20 mg are recommended to be discontinued from study.

All dose changes must be recorded on the Dosage Administration Record CRF. Table 7 outlines the dose reduction steps for pasireotide.

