**Thrombocytopenia**

Grade 1 (PLT < LLN - 75,000/mm  )	Maintain dose level
Grade 2 (PLT < 75,000 - 50,000/mm  )	Maintain dose level
Grade 3 (PLT < 50,000 - 25,000/mm  )	Omit dose until resolved to ≤ Grade 1, then ↓ 1 dose level 
 
• If resolved ≤ 7 days, then maintain dose level
 
• If resolved > 7 days, then ↓ 1 dose level
 

Grade 4 (PLT < 25,000/mm  )	Omit dose until resolved to ≤ Grade 1, then ↓ 1 dose level
Febrile neutropenia (ANC < 1.0 x 10  /L, fever ≥ 38.5°C)	Omit dose until resolved, then ↓ 1 dose level

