**Renal****Serum creatinine**

< 2 x ULN	Maintain dose level
2-3 x ULN	Omit dose until resolved to ≤ Grade 1, then 
 
• If resolved ≤ 7 days, then maintain dose level
 
• If resolved > 7 days, then ↓ 1 dose level
 

Grade 3 (> 3.0 - 6.0 x ULN)	Omit dose and discontinue patient from study treatment
Grade 4 (> 6.0 x ULN)	Omit dose and discontinue patient from study treatment

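### Three hematologic rows of Table 7 both reduce and maintain the dose when the event resolves within 7 days

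*Combined protocol and SAP*

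**What the plan says.** Section 6.6 sends the reader to the table for the rule: "Table 7 outlines the dose reduction steps for pasireotide". Section 6.5 does the same, and section 6.5.1 describes what follows as guidelines. The table covers both arms under the heading "Recommended dose modifications for pasireotide/ placebo".

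The rows for grade 3 and grade 4 neutropenia share one lead line, "Omit dose until resolved to ≤ Grade 2, then ↓ 1 dose level", followed by two bullets: "If resolved ≤ 7 days, then maintain dose level" and "If resolved > 7 days, then ↓ 1 dose level". The grade 3 thrombocytopenia row has the lead line "Omit dose until resolved to ≤ Grade 1, then ↓ 1 dose level" and the same two bullets.

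Three other provisions bear on these rows:
- Sections 6.5 and 6.6 let a patient whose dose was reduced go back up once the tolerability problem has resolved.
- The same sections name 20 mg as the minimum dose and recommend discontinuation for patients who cannot tolerate it.
- Section 6.8 requires the study drug to be stopped for hematology or chemistry abnormalities of CTC grade 3 or above that the investigator considers clinically significant.

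**The concern.** Each of the three lead lines is a complete instruction to reduce the dose once the count has recovered, with no condition attached. The first bullet beneath it tells staff to keep the dose if recovery came within 7 days. For that outcome the cell gives two different doses and no order of precedence.

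This is a safety rule, applied to both arms during the blinded year. Two staff members who both follow the table could give the next injection at different levels after the same event, and both could claim to have complied. Protocol adherence for such an event could not be judged from the document. The dose received would then depend partly on who read the table.

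**Working it through.** The protocol has no figure to reproduce here, so the check is a row-by-row reading of Table 7.

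**Step 1. The three rows, by time to resolution.**

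| Row | Lead line | Bullet, ≤ 7 days | Bullet, > 7 days | Consistent? |
|---|---|---|---|---|
| Neutropenia grade 3 | Omit to ≤ grade 2, reduce one level | Maintain | Reduce one level | ≤ 7 days: no; > 7 days: yes |
| Neutropenia grade 4 | Omit to ≤ grade 2, reduce one level | Maintain | Reduce one level | ≤ 7 days: no; > 7 days: yes |
| Thrombocytopenia grade 3 | Omit to ≤ grade 1, reduce one level | Maintain | Reduce one level | ≤ 7 days: no; > 7 days: yes |

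The instruction to omit the dose until recovery is unambiguous in all three rows. Only the dose on resumption, after recovery within 7 days, is in dispute.

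**Step 2. The other rows that omit and then resume.** They use one of two forms, and neither contradicts itself.
- Reduction with no bullets: for example grade 4 thrombocytopenia and febrile neutropenia.
- Bullets only: creatinine at 2-3 x ULN, bilirubin grades 2 and 3, and asymptomatic amylase or lipase grade 3. In the creatinine row the lead line stops at "Omit dose until resolved to ≤ Grade 1, then" and leaves the action to the bullets.

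No other row combines an unconditional reduction with a bullet to maintain, so the count of three is exact. The same pattern in three separate rows is unlikely to come from PDF extraction.

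**Step 3. Does another section settle it?** Sections 6.5 and 6.6 refer back to the table, and 6.5.1 only introduces it. None ranks the lead line against the bullets. Section 6.8 calls for discontinuation of events judged clinically significant. All three rows concern grade 3 or 4 hematology, so that is a third possible action. It removes the reduce-or-maintain question for events so judged and leaves it open for the rest.

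**Step 4. Size of the difference at the next injection.** The levels are 60, 40 and 20 mg.
- From 60 mg: maintain gives 60, reduce gives 40. Difference (60 − 40)/60 = 20/60 = 33%.
- From 40 mg: maintain gives 40, reduce gives 20. Difference (40 − 20)/40 = 20/40 = 50%.
- From 20 mg: maintain gives 20. No lower level exists, so the table does not define a reduced dose.

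The documents give no frequency for these events, so no expected number of affected patients can be calculated.

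**The case against.** The strongest reply is that the bullets plainly qualify the lead line. They sit beneath it and split it by time to resolution. If the lead line governed alone, the ≤ 7-day bullet would do nothing, and rows meant as a plain reduction carry no bullets. That is a coherent reading, but the text does not state it, and it leaves the reduction in the lead line without a function when the creatinine and bilirubin rows omit those words. The reverse is also possible: a plain reduction, as for grade 4 thrombocytopenia, into which bullets were copied. The documents do not decide between them, and the creatinine row does not show which was meant.

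It is also fair to say that the table is a guideline with a recommended status. That softens the conflict, but a recommendation still has to state one action.

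Three stronger readings might be inferred, and the documents do not support them:
- *The rows cannot be followed at all.* They can for resolution after 7 days, and the omission step is clear throughout.
- *The dose gap persists at every later injection.* Sections 6.5 and 6.6 permit a return to the higher dose after resolution, and in the disputed case the event has already recovered to the grade named in the row. The return is optional, so a gap is possible but need not last.
- *The efficacy result is compromised.* The primary analysis in section 10.2 follows intent-to-treat principles and does not use dose level. In the placebo arm during year 1 no active dose is at stake.

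Reach is probably small. Entry requires an ANC of at least 1.5 and platelets of at least 100 x 10⁹/L, and the LAR experience summarised in section 1.5 does not mention either event. This limits the consequence and leaves the contradiction in place.

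**Conclusion.** The point holds as a wording contradiction in a safety dosing rule. It is confined to three rows and to events that resolve within 7 days. For those events the table gives two doses that differ by 20 mg, which is 33% of a 60 mg dose or 50% of a 40 mg dose, and at 20 mg one of the two instructions has no defined dose. Section 6.8 narrows the affected cases to abnormalities not judged clinically significant, and it adds a third action that the table does not mention.

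The practical weight is low, on the assumption that these events are uncommon, since the documents give no rate. The power calculation and the primary analysis are not affected. No view is taken on which dose action is correct.

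**What to change.** The sponsor should reconcile the lead lines and bullets of the grade 3 neutropenia, grade 4 neutropenia and grade 3 thrombocytopenia rows, so that resolution within 7 days and resolution after 7 days each have one stated action. The same edit should make the rows consistent with section 6.8, stating when discontinuation takes precedence over the table. It should also make clear what applies to a patient already at the 20 mg minimum. The choice of action in each case belongs to the sponsor.

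The cost is a wording change to three table rows with a cross-reference to section 6.8. Sample size, visits and analysis do not change. Because the table is a dosing rule, the edit should go through the amendment process in section 9.

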**Thrombocytopenia**

Grade 1 (PLT < LLN - 75,000/mm  )	Maintain dose level
Grade 2 (PLT < 75,000 - 50,000/mm  )	Maintain dose level
Grade 3 (PLT < 50,000 - 25,000/mm  )	Omit dose until resolved to ≤ Grade 1, then ↓ 1 dose level 
 
• If resolved ≤ 7 days, then maintain dose level
 
• If resolved > 7 days, then ↓ 1 dose level
 

Grade 4 (PLT < 25,000/mm  )	Omit dose until resolved to ≤ Grade 1, then ↓ 1 dose level
Febrile neutropenia (ANC < 1.0 x 10  /L, fever ≥ 38.5°C)	Omit dose until resolved, then ↓ 1 dose level

**Renal****Serum creatinine**

< 2 x ULN	Maintain dose level
2-3 x ULN	Omit dose until resolved to ≤ Grade 1, then 
 
• If resolved ≤ 7 days, then maintain dose level
 
• If resolved > 7 days, then ↓ 1 dose level
 

Grade 3 (> 3.0 - 6.0 x ULN)	Omit dose and discontinue patient from study treatment
Grade 4 (> 6.0 x ULN)	Omit dose and discontinue patient from study treatment

**Hepatic See also section 7.5.4.1****Bilirubin**

Grade 1 (< 2 x baseline value)	Maintain dose level
Grade 2 (2-3 x baseline value)	Omit dose until resolved to ≤ Grade 1, then 
 
• If resolved ≤ 7 days, then maintain dose level
 
• If resolved > 7 days, then ↓ 1 dose level
 

Grade 3 (> 3.0 - 10.0 x ULN)	Omit dose until resolved to ≤ Grade 1, then 
 
• If resolved ≤ 7 days, then maintain dose level
 
• If resolved > 7 days, then ↓ 1 dose level
 

Grade 4 (> 10.0 x ULN)	Omit dose and discontinue patient from study treatment

NOTE: If grade 3 or 4 hyperbilirubinemia is due to the indirect (unconjugated) component only, and hemolysis as the etiology has been ruled out as per institutional guidelines (e.g. review of peripheral blood smear and haptoglobin determination), then ↓ 1 dose level and continue treatment at the discretion of the investigator

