 Height required only at pre-study 12 lead ECG & interpretation at screening and ½ hour after first injection. Repeat ECG on 21st day after injection for the first 3 months then every third month. All ECGs are faxed to the Mayo Clinic ECG Core lab. Includes WBC with differential Comprehensive fasting metabolic panel includes: albumin, total bilirubin, calcium, CO2, (bicarbonate) chloride, creatinine, BUN, potassium, total protein, sodium, AST, ALT, ALP,, and glucose. Liver function tests are assessed at baseline (if baseline LFTs are **done within 7 days of day 1 of treatment** they do not have to be repeated on day 1), day 22 after first injection, day 29, day 50, 57 and 85. After day 85 and the 4th LAR Injection, monitoring should follow the existing protocol schedule. Day 22 & 50 LFTs must be available & assessed prior to dosing on days 29 (2nd injection) and 57 (3rd injection). Only in patients with associated PKD. Hemoglobin A1C is done at baseline and 3 monthly Thyroid function is also acceptable if checked within 30 days of the screening visit Bi-weekly cyclosporin levels will be monitored for the first month in enrolled patients who are on this medication (mail in test) Plasma glucose is required 6 hours after first injection. Monitor FPG or finger stick at baseline and at 21st day of treatment for first 3 months. Monitor FPG or finger stick monthly (or as clinically appropriate), thereafter.

-  Women of childbearing potential only (urine pregnancy test). If CT scan is needed, a negative pregnancy result will need to be obtained prior to performing the CT. For women of child bearing potential who will be having an MRI – a pregnancy test is not required at month 12.
-  SOM230/placebo IM injections will be given every 28 days, +/- 2 days.
-  No gallstone assessment is needed on visits where MRI is performed, as gallstones will be detected on MRI if present.
-  In year 2, safety assessments for patients crossing over from placebo to SOM 230 will be required. These will be per the same schedule after the first SOM230 injection as was performed in year 1 for all patients enrolled.

At a minimum the following safety evaluations (Table 9) are to be included in all protocols.

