### 7.5.1 Adverse events

An adverse event for the purposes of this protocol is the appearance of (or worsening of any pre-existing) undesirable sign(s), symptom(s), or medical condition(s) occurring after signing the informed consent even if the event is not considered to be related to the study drug(s). Please refer to the adverse event section of the protocol for the protocol-specific definitions of study drug and study treatment.

Adverse events will be assessed according to the Common Toxicity Criteria for Adverse Events [CTCAE] version 3.0. If CTCAE grading does not exist for an adverse event, the severity of mild, moderate, severe, and life-threatening, or grades 1 - 4, will be used. CTCAE grade 5 (death) will not be used in this study; rather, this information will be collected in the End of Treatment. Adverse event monitoring should be continued for at least 4 weeks following the last dose of study treatment.

Adverse events (but not serious adverse events) occurring before starting study treatment but after signing the informed consent form are recorded on the Medical History/Current Medical Conditions Electronic Case Report Form. Abnormal laboratory values or test results constitute adverse events only if they induce clinical signs or symptoms, are considered clinically significant or require therapy (e.g., any hematologic abnormality that requires transfusion or cytokine treatment); and should be recorded on the Adverse Events CRF under the signs, symptoms or diagnosis associated with them. In addition, isolated abnormal laboratory values that are considered clinically significant (e.g., cause study discontinuation or constitutes in and of itself a Serious Adverse Event) should be recorded on the Adverse Events CRF. SAEs occurring after signing the Informed Consent are recorded on the Adverse Event CRF.

The occurrence of adverse events should be sought by non-directive questioning of the patient at each visit during the study. Adverse events also may be detected when they are volunteered by the patient during or between visits or through physical examination, laboratory test, or other assessments. As far as possible, each adverse event should be evaluated to determine:

1. The severity grade (CTCAE grade 1-4)
2. Its relationship to each study drug (suspected/not suspected)
3. Its duration (start and end dates or if continuing at final exam)

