#### **7.5.4.1 Abnormal liver function management:**

Perform within 72 hours of awareness of abnormal LFTs:

Perform liver-directed medical history and physical examination (i.e. assess occupational hazards, concomitant medications including OTC meds, intercurrent illness, etc)

Liver chemistry tests: ALT, AST, total bilirubin, (fractionate to direct/indirect bilirubin if total bilirubin is > 2.0x ULN), Alb, PT (INR), ALP, and GGT

Perform hepatitis screen: anti-HAV, IgM (to confirm acute hepatitis A), HbsAg, Anti-HBc, anti-HCV (if positive PCR viral load should be assessed), Anti-HEV, ANA antibodies, anti-smooth muscle anti-bodies, CMV, EBV

Perform abdominal ultrasound (liver and biliary tree)

Liver chemistry tests should be monitored every 3-4 days for LAR studies until resolution or return to baseline status.

For ALT or AST > 5x ULN and ≤ 8x ULN:

- Study medication should be temporarily interrupted and liver chemistry tests monitored **every 3-4 days** until resolution or return to baseline
- If resolution or return to baseline does not occur after 2 weeks, the patient should be discontinued.
- If ALT or AST returns to less than 5x ULN, study drug can be resumed and patient can continue study per protocol
- If ALT or AST rises above 5x ULN anytime after study drug is resumed, then study drug should be discontinued immediately.

Resolution return to baseline does not occur after two weeks the patient should be discontinued

If ALT or AST rises about 5X ULN anytime after study drugs resumed and study drug to be discontinued immediately

Study medication should be discontinued immediately if any of the discontinuation criteria below are met: (see appendix 4)

ALT or AST > 3x ULN and Total Bilirubin ≥ 2x ULN and ALP < 2x ULN

ALT or AST > 5x ULN and ≤ 8x ULN persistent for more than 2 weeks

ALT or AST > 8x ULN

Re-challenge of study medication is prohibited once discontinuation criteria are met.

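### Table 7 grades bilirubin against baseline in grades 1-2 and against ULN in grades 3-4, so its printed limits leave a gap and can hold the dose at normal values: a minor wording correction to two rows

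*Combined protocol and SAP*

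**What the plan says.** Table 7 (Section 6.6) gives four bilirubin rows. Grade 1 is below 2 x baseline, dose maintained. Grade 2 is "Grade 2 (2-3 x baseline value"). Grade 3 is "Grade 3 (> 3.0 - 10.0 x ULN"). Grade 4 is above 10 x ULN, with discontinuation. Grades 2 and 3 share one instruction, "Omit dose until resolved to ≤ Grade 1, then", followed by the same rule: same dose if resolved within 7 days, one level lower if later. A note under the rows allows treatment to continue one level lower, at the investigator's discretion and once hemolysis is excluded. It applies "If grade 3 or 4 hyperbilirubinemia is due to the indirect (unconjugated) component only".

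The table is headed "Recommended dose modifications for pasireotide/ placebo", and its opening row keeps the dose when there is no toxicity. Section 5.2.1 admits a bilirubin up to 1.5 x ULN and sets no lower limit. Footnote 4 to Table 8 ties liver tests to dosing: "Day 22 & 50 LFTs must be available & assessed prior to dosing on days 29" and 57.

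**The concern.** The reference value changes between grade 2 and grade 3, so the rows join up only when baseline equals ULN. The creatinine rows just above use ULN throughout and run on without a break.

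The rows are read when an injection is about to be given or withheld, and the injection is a 28-day depot. In the gap, staff must infer the action. With a low-normal baseline, the literal grade 2 row withholds drug at a bilirubin that is not abnormal, which conflicts with the no-toxicity row. If such a hold lasts more than 7 days, the dose also falls one level.

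No other section supplies a specific dose rule for an isolated bilirubin in the gap. The named bilirubin criterion in Sections 6.8 and 7.5.4.1 and Appendix 4 also requires raised ALT or AST and an ALP condition. The general laboratory criterion in Section 6.8 starts at grade 3 and rests on the investigator's judgment.

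**Working it through.** The plan gives no figure to reproduce; this is a check of interval coverage.

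**Inputs.** Limits from the Table 7 bilirubin rows; eligible baselines up to 1.5 x ULN from Section 5.2.1. Let b be baseline and x the current bilirubin, both in multiples of ULN.

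**Rows as printed.** Grade 1: x < 2b. Grade 2: 2b ≤ x ≤ 3b. Grade 3: 3 < x ≤ 10. Grade 4: x > 10.

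**Gap.** Values with 3b < x ≤ 3 meet no row. Such values exist only if 3b < 3, that is b < 1. The width is 3 - 3b: 2.1 at b = 0.3, 1.8 at 0.4, 1.5 at 0.5 and 0.6 at 0.8.

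**Hold at a normal value.** Grade 2 reaches x ≤ 1 only if 2b ≤ 1, that is b ≤ 0.5. Re-dosing requires x < 2b, so at b = 0.3 it is barred until bilirubin is below 0.6, and at b = 0.4 until below 0.8.

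**Overlap.** If b > 1, values with 3 < x ≤ 3b meet both grade 2 and grade 3.

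**Proposed rows.** Grade 1: x < 2b or x ≤ 1. Grade 2: x ≥ 2b and 1 < x ≤ 3. Grades 3 and 4 unchanged.

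| b | Grade 2 now | Normal values held now | No row now | Two rows now | Grade 2 after the edit |
|---|---|---|---|---|---|
| 0.3 | 0.6-0.9 | 0.6-0.9 | >0.9-3.0 | none | >1.0-3.0 |
| 0.4 | 0.8-1.2 | 0.8-1.0 | >1.2-3.0 | none | >1.0-3.0 |
| 0.5 | 1.0-1.5 | 1.0 only | >1.5-3.0 | none | >1.0-3.0 |
| 0.8 | 1.6-2.4 | none | >2.4-3.0 | none | 1.6-3.0 |
| 1.0 | 2.0-3.0 | none | none | none | 2.0-3.0 |
| 1.2 | 2.4-3.6 | none | none | >3.0-3.6 | 2.4-3.0 |
| 1.5 | 3.0-4.5 | none | none | >3.0-4.5 | 3.0 only |

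The edited rows are exhaustive and exclusive for every eligible baseline. For x ≤ 3, grade 2 is exactly the complement of grade 1; since 2b ≤ 3 when b ≤ 1.5, grade 1 never runs into grade 3.

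**Alternatives.**
- Putting ULN into the grade 2 row alone fails. It opens a new gap from 2b to 2 x ULN when b < 1 (at b = 0.5, from 1.0 to below 2.0), and a maintain-or-omit conflict when b > 1 (at b = 1.5, from 2.0 to below 3.0).
- Stretching grade 2 from 2 x baseline to 3 x ULN closes the gap but still holds at normal values when b ≤ 0.5.
- Putting both lower rows in ULN closes everything but drops existing holds at abnormal values: >1.0-1.2 at b = 0.4, >1.0-1.5 at b = 0.5, and 1.6 to below 2.0 at b = 0.8.

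**The case against.** The strongest reply is that the gap changes few decisions. A value in it has already passed the grade 2 trigger, and the rows on both sides say the same thing, so omission is the natural reading. Table 7 also points to Section 7.5.4.1, which requires a work-up of abnormal liver tests within 72 hours and then: "Liver chemistry tests should be monitored every 3-4 days for LAR studies until resolution or return to baseline status". Section 6.8 lets the investigator stop drug for any clinically significant laboratory change. All of this stands, and it limits the weight of the point.

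Second, Sections 6.5.1 and 7.5.1 grade toxicity by CTCAE v3.0, and the row labels in Table 7 are CTCAE grades with a value in brackets. A site that assigned the CTCAE grade first might never meet the gap. The CTCAE bilirubin limits are not printed in the documents, so this can be neither confirmed nor excluded. The gap is established only for the printed limits.

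Third, the table concerns patients with adverse events, and Section 7.5.1 sets a threshold even for abnormal results: "Abnormal laboratory values or test results constitute adverse events only if they induce clinical signs or symptoms", are judged clinically significant, or need therapy. A normal bilirubin is further still from that. This favors dosing, but the explicit grade 2 limits say the opposite, so the text conflicts with itself.

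A reader might infer more: that patients would be dosed through a rising bilirubin, or that many injections would be withheld without cause and the treatment contrast weakened. The documents support neither. The first ignores the identical neighboring actions and the work-up rule. The second needs a distribution of baseline bilirubin, which the documents do not give.

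**Conclusion.** The inconsistency is real and follows from the printed limits alone. There is no row above 3 x baseline up to 3 x ULN when baseline is below ULN, and there is a literal hold at normal values when baseline is at or below 0.5 x ULN. Both kinds of baseline are eligible. The conclusion assumes that staff apply the bracketed limits as printed rather than CTCAE v3.0 limits. How often either situation would arise cannot be stated. This is a minor correction to a safety table; it has no bearing on the primary endpoint, sample size or analysis.

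**What to change.** Change the limits of two bilirubin rows in Table 7:

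- Grade 1: below 2 x baseline, or at most ULN. Maintain dose.
- Grade 2: at least 2 x baseline and above ULN, up to 3.0 x ULN. Omit until grade 1 or lower, with the existing 7-day rule.

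Leave grades 3 and 4 and the combined ALT/AST-bilirubin-ALP criterion as they are. State that the bracketed limits govern the dose decision.

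The cost is wording only, with three consequences to state openly:

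- Rises that stay at or below ULN no longer trigger a hold or block re-dosing. This includes the part of the present gap that lies in the normal range. At a baseline of 0.3 x ULN the affected values are 0.6-1.0 x ULN; at 0.4, 0.8-1.0; at 0.5, 1.0 only.
- Gap values above ULN become explicit grade 2 holds, and the note on indirect bilirubin covers grades 3 and 4 only. At a baseline of 0.4 x ULN, an indirect-only rise to 2 x ULN would be held, while one to 4 x ULN could continue one level lower. The present grade 2 row already has this anomaly and the edit widens it, so the sponsor should decide whether the note should also cover grade 2.
- For baselines above ULN, values above 3.0 x ULN and up to 3 x baseline become grade 3 only, so the note's exception can then apply to them. At a baseline of 1.5 x ULN these are values above 3.0 and up to 4.5 x ULN.
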